SAE	Serious Adverse Event
SD	Standard Deviation
SE	Standard Error
SSI	Significant Safety Issue
SD	Stable Disease
SUSAR	Suspected Unexpected Serious Adverse Reaction
TPP	Time to progression

1. ADMINISTRATIVE INFORMATION

Protocol: ACCT008/ASSG35; Version 5; 18Sep2020

Novartis Ref: CLBH589XAU13T

[figure not shown]
[figure not shown]
ClinicalTrials.gov Identifier: NCT04897880

1.1 Document Version History

Version Date	Version	Author	Signature	Change Description	Reason/Comment
December 2024	1.0	AR		Initial release.	Not applicable.

2. STUDY SYNOPSIS

This is a multi-centre, open-label, single-arm Phase 2 study in participants < 40 years old with refractory solid and CNS tumours. Participants were stratified by tumour type: osteosarcoma, neuroblastoma, and malignant rhabdoid tumour or atypical teratoid rhabdoid tumours (ATRT/MRT). Eligible participants included those with refractory or relapsed osteosarcoma, neuroblastoma and MRT/ATRT, or newly diagnosed MRT/ATRT that were stable after completion of standard therapy. Participants must have had histologic verification of the diagnosis of malignancy at either the time of initial diagnosis or at relapse. A maximum of 60 participants (20 per strata) were planned to be treated with panobinostat as a continuous oral dose starting at 10 mg/m² per day. Study treatment was planned to continue until disease progression, intolerable toxicity, or participant decision for a maximum of one year (12 treatment courses of 28 days duration each). Patients will be followed for up to 2 years from completion of study therapy.

The study design schematic is presented in Figure 2.1-1

Schedule of Analyses:

The dose evaluation and study expansion analyses in each strata were evaluated separately to this SAP. They are described below.

Dose Evaluation

The biological activity of panobinostat at a given dose level was determined by the real-time acetylation status (as defined by acetylated H4 on Peripheral Mononuclear Cells (PMNCs) at day eight compared with pre-treatment. This analysis was performed for a minimum of 2 patients in each strata at the required dose levels. Once biological activity was confirmed via the acetylation status of H4 on PMNC at any dosing level in any strata, it did not need to be repeated and dosing adjustments could be made on dose limiting toxicities (DLTs) and adverse events (AEs) alone.

- i) If significant increase in acetylation, and therefore biological activity, was demonstrated at the starting dose of 10 mg/m² then no dosing adjustment took place unless DLTs/AEs were observed.
- ii) In the case of drug toxicity and irrespective of biological activity, intra-patient dose reductions in 2 mg/m² increments were applied, and the dose level for the strata reviewed.
- iii) In the case of inadequate biological activity, with no toxicity, intra-patient dose escalations of 2 mg/m² were recommended.

The final dose per strata was the level where continuous dosing was maintained for a 4-week period with acceptable toxicity and biological effect. The final Panobinostat doses were 6mg/m² per day for the ATRT/MRT cohort, 8mg/m² per day for the neuroblastoma cohort, and 4mg/m² per day for the osteosarcoma cohort.

Study Expansion

The study employed a Simon two-stage minimax design (1). At trial design stage an initial efficacy analysis was planned when a minimum of 9 patients in each strata were enrolled. The regimen would be considered worthy of further study if disease stability at 4 months was observed in 3 or more of the first 9 patients in a stratum and less than 30% of patients experience a DLT at the final dose level. If this was achieved, recruitment would proceed to a total of 20 patients in each strata.

However, due to uncertainty of panobinostat supply, a decision was made to permanently close the osteosarcoma and neuroblastoma arms prior to the initial efficacy analysis when 9 and 2 had been enrolled in the osteosarcoma and neuroblastoma arms, respectively. At that time, it was decided to continue recruitment into the ATRT/MRT cohort who had met the initial efficacy criteria for 3/9 participants with disease stability and <30% experiencing a DLT at the final dose level. The ATRT/MRT arm closed in December 2021 due to termination of the study supply agreement, at that time 14 participants had been enrolled in the ATRT/MRT arm.

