2.2.2 SECONDARY ENDPOINTS

a) Efficacy as measured by Clinical Benefit Rate (percentage of patients with stable disease or better using MRI/CT imaging) at 6 and 12 months after intervention commencement. Stable disease is defined as MRT/ATRT/Osteosarcoma with complete response (CR), partial response (PR), minor response (MR), stable disease (SD) overall response. Neuroblastoma with CR/PR/SD or Non-CR/Non-PD overall response.

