2.4 INTERVENTION

A three-week washout period was required after conventional myelosuppressive chemotherapy and/or biologic therapy to start Panobinostat therapy.

Panobinostat was supplied in capsule form and administered orally. Each course consisted of 4 weeks (28 days). Treatment will continue for up to 12 months consisting of 12 treatment courses, each of 4 weeks (28 days) duration.

Intra-patient dose adjustments of 2 mg/m² were made to a starting dose of 10 mg/m² based on DLTs/AEs and biological activity, and dose level for that stratum reviewed. For full criteria for dose escalation and reduction see protocol version 5.0 18Sep2020. The final dose per strata was the level where continuous dosing is maintained for a 4-week period with acceptable toxicity and biological effect.

Protocol therapy could be terminated for the following reasons: a)
Progressive disease (radiographic or clinical)

- b) Irreversible or unacceptable dose-limiting toxicity
- c) Other adverse event
- d) Refusal of further protocol therapy by patient or parent/guardian
- e) Physician determines it is not in the patient's best interest
- f) Pregnancy
- g) Termination or suspension of clinical trial

The investigator's clinical judgment was used to determine whether a subject should be removed from treatment or from the study due to progressive disease, AE or DLT, or another reason.

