2.6 SAMPLE SIZE

The study employed a Simon two-stage minimax design (1). A 30% gain in Clinical Benefit Rate (CBR) was considered as the minimum gain required to warrant further study of this regimen. In this case the clinical benefit to be observed is stability of disease. 70% stability at 4 months would be indicative of clinical utility, whereas a rate of 40% would be the lower limit of interest, with $\alpha = .15$ and $\beta = .10$. The minimal accrual number required in each strata was 14 patients. This was increased to 20 patients in each strata, over 3 years, for a total of 60 patients.

The biological activity analysis was performed for a minimum of 2 patients in each strata at the required dose levels.

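### The stage-1 gate of 3 or more of 9 is one lower than the minimax bound the stated inputs give (4 or more of 9), and the 4-month rate that sized the trial is not among the outputs

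*SAP*

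**What the plan says.** Section 2 (Study Expansion) and section 2.6 both name a Simon two-stage minimax design. Section 2.6 sets the error limits (alpha .15, beta .10) and gives the rates: "70% stability at 4 months would be indicative of clinical utility, whereas a rate of 40% would be the lower limit of interest". It continues: "The minimal accrual number required in each strata was 14 patients", and then "This was increased to 20 patients in each strata, over 3 years, for a total of 60 patients".

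Section 2 places the first efficacy look at 9 patients per stratum. Expansion to 20 requires that "disease stability at 4 months was observed in 3 or more of the first 9 patients in a stratum", together with a dose-limiting toxicity rate under 30% at the final dose. The osteosarcoma and neuroblastoma arms closed before that look. Recruitment went on in the MRT/ATRT cohort, "who had met the initial efficacy criteria for 3/9 participants with disease stability" and an acceptable toxicity rate, until supply ended with 14 enrolled. No final success bound is given for 14 or for 20 patients.

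Sections 2.2.2 and 6.1.1 and Table 12 report the clinical benefit rate only "at 6 and 12 months after intervention commencement".

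**The concern.** In Simon's notation r1 is a stopping value: a stratum stops at r1 or fewer and continues at r1 + 1 or more. A gate of 3 or more therefore means r1 = 2. If the named design has r1 = 3, the SAP continues at the count on which that design stops. Reading the stopping value as a continuation value would produce this difference, although the SAP does not say how the gate was set.

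A reader of the report would take the gate that MRT/ATRT met as the futility bound of a minimax design, and so as a stronger screen than it was. The same reader, told that the trial was sized to separate 40% from 70% stability at 4 months, would find no 4-month result to compare with those rates.

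**Working it through.** **Inputs.** p0 = 0.40, p1 = 0.70, alpha = .15, beta = .10 and N = 14 (section 2.6); n1 = 9 and continuation at 3 or more (section 2). Alpha is taken as one-sided, which is an assumption. Only the efficacy part of the gate is computed; the toxicity condition is left out.

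**Formula.** For a design (r1/n1, r/N), with X the stage-1 count and Y the count among the remaining N − n1 patients:

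P(success | p) = Σ over x = r1+1 … n1 of P(X = x) × P(Y ≥ r + 1 − x)

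Alpha is this value at p0 and power is this value at p1. Expected N = n1 + (N − n1) × P(X > r1).

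**Step 1: reproduce the plan's 14.** Enumerating all two-stage designs, none up to N = 13 meets alpha ≤ .15 and power ≥ .90. At N = 14 six do, all with r = 7. The one with the smallest expected N at 40% is 3/9, 7/14, and it is the only one with n1 = 9:

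- alpha 0.1476, power 0.9032
- expected N at 40%: 9 + 5 × (1 − 0.4826) = 11.59

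The SAP's 14 and 9 both come out. The matching rule is to stop at 3 or fewer of 9, continue at 4 or more, and declare activity at 8 or more of 14.

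**Step 2: the written gate at N = 14.** With r1 = 2 and 8 or more of 14, the only added route to success is 3 of 9 followed by 5 of 5:

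- at 40%: 0.2508 × 0.4⁵ = 0.0026, so alpha = 0.1476 + 0.0026 = 0.1501
- power 0.9067
- expected N at 40%: 9 + 5 × (1 − 0.2318) = 12.84

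With 2 of 9, the most that can be reached is 2 + 5 = 7, below 8. The written gate then stops only when success is already impossible, and its alpha and power equal those of a single-stage rule of 8 or more of 14.

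**Step 3: chance of stopping at stage 1.**

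| True rate | Written gate, P(X ≤ 2) | Recomputed bound, P(X ≤ 3) |
|---|---|---|
| 30% | 46.3% | 73.0% |
| 40% | 0.0101 + 0.0605 + 0.1612 = 23.2% | 23.2% + 25.1% = 48.3% |
| 70% | 0.4% | 2.5% |

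**Step 4: the planned N = 20.** The SAP gives no final bound, so 11 or more of 20 is assumed here:

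| Gate | Alpha | Power | Expected N at 40% |
|---|---|---|---|
| 3 or more of 9 | 0.127 | 0.951 | 9 + 11 × 0.7682 = 17.5 |
| 4 or more of 9 | 0.119 | 0.939 | 9 + 11 × 0.5174 = 14.7 |

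Both gates meet both limits.

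**Step 5: the endpoint.** Section 2.6 sizes on stability at 4 months. Section 6.1.1 and Table 12 list 6 and 12 months, and no other output gives a 4-month rate. Scans are 2-monthly (section 2.7), so the data should exist.

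**The case against.** The strongest reply is that the executable plan was 9 and then 20, not 9 and then 14. The bound of 4 or more belongs to the 14-patient design before the increase, and at 20 the written gate can hold both error limits. That stands, and it limits the point to a wrong label and weaker early stopping.

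A second reply is scope. Section 2 says the expansion analyses were evaluated separately from this SAP, the MRT/ATRT arm closed in December 2021, and the SAP dates from December 2024. The gate is history and no analysis uses it. That also stands, which is why the remedy is disclosure. The SAP nevertheless restates the design, its inputs, the gate and the outcome, and these do not agree. The separate evaluation explains why the interim result is absent, but not why no final 4-month rate is planned.

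Three stronger readings are tempting and are not supported:

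- **The written gate and 14 patients cannot belong to one design.** With 8 or more of 14, alpha is 0.1501 against a limit written as .15. That excess is at rounding level. The sound statement is that the gate is not the minimax choice.
- **MRT/ATRT continued on a result that should have stopped it.** The reference to 3/9 may give the observed count or only restate the criterion. The cohort met the criterion as written, and the SAP does not expressly claim that a Simon bound was cleared.
- **Type I error was inflated.** At 20 patients it need not be.

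**Conclusion.** The concern holds as a minor one. The stated inputs, with one-sided alpha and exact binomial calculation, lead to 4 or more of 9 and 8 or more of 14; the SAP's gate is one patient lower and is not the minimax bound. The cost is futility stopping: at a true rate of 40%, roughly half the chance of stopping at stage 1 is lost (48.3% to 23.2%). It bears on MRT/ATRT alone, since the other two arms never reached the look, and it does not touch EFS, OS or safety. If the observed stage-1 count was exactly 3, it equals the stopping value of the recomputed design, so the count needs confirming. The missing 4-month rate is a separate and equally modest gap: without it the results cannot be set against the 40% and 70% that justified the sample size.

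**What to change.** 1. In sections 2 and 2.6, state that the gate applied (3 or more of 9) was looser than the minimax bound recomputed from the stated inputs (4 or more of 9; 8 or more of 14), labelled as a recomputation. Give the stopping probabilities at 40% and 30%, confirm the observed MRT/ATRT stage-1 count, and do not describe the expansion as clearing a Simon minimax bound.
2. In section 6.1.1 and Table 12, add a descriptive 4-month stability proportion with an exact 95% CI for MRT/ATRT (14 enrolled) and osteosarcoma (9 enrolled). Use the month length in section 3.7 (4 × 30.4375 = 121.75 days) and the same assessment rules as the 6- and 12-month rows. Read it against 40% and 70% with no pass/fail test.

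The cost is a few sentences and one table row from scans already scheduled. The downside is a less favourable account of stage 1 and a wide interval. As illustrations only, 8/14 gives 28.9% to 82.3% and 3/9 gives 7.5% to 70.1%; each covers both 40% and 70%.

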2.1 OBJECTIVES

2.1.1 PRIMARY OBJECTIVES

The primary aims of this study are as follows:

- a) To define the anti-tumour activity of low dose continuous panobinostat.
- b) To define and describe the toxicities of panobinostat for patients on a continuous dosing schedule.

2.1.2 SECONDARY OBJECTIVES

The secondary aims are:

- a) To define the anti-tumour activity of low dose continuous panobinostat using functional imaging techniques.
- b) To assess the biologic activity of low dose panobinostat by measuring histone acetylation status in peripheral mononuclear cells (PMNC), bone marrow and fresh tumour tissue specimens in all patients (when available).

2.2 ENDPOINTS

2.2.1 PRIMARY ENDPOINTS

- a) Estimated 2-year Event free survival (EFS). EFS is calculated as the time from study enrolment to first documented disease progression, relapse or second malignancy, or death from any cause
- b) Estimated 2-year Overall Survival (OS). OS is calculated as the time from study enrolment to death from any cause.
- c) Safety, as assessed by incidence of adverse events graded according to the NCI-CTCAE, version 4.0 [Time Frame: 1 week to 12 months after intervention commencement]

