2.7 STUDY PROCEDURES

All entry requirements had to be completed during the four-week screening period before study enrolment.

Studies to be Obtained	Pre-salvage therapy ^a	Screening prior to enrolment (Baseline)	Weeks 1-4 (first 28 day course)	Subsequent Months (28 day courses)	Follow-up ^b
History (including AEs/DTs)		X	Weekly	X	X
Physical Exam (height, weight, BSA)		X	Weekly	X	X
Performance Status Refer to Appendix I		X	Weekly	X	X
Full Blood Evaluation (FBE) with Differential & Blood Film		X	Weekly	X	X
Urinalysis ^c		X	Weekly	X	
Urea & Electrolytes Calcium, Magnesium & Potassium		X	Weekly	X	X
Renal Function/GFR/Creatinine		X	Weekly	X	X
Liver Function Tests including Total Protein & Serum Albumin		X	Weekly	X	X

Thyroid Function Tests (TFTs including TSH, T3, T4)		X		End of therapy	
CT/MRI of Primary Tumour^d	X	X		2 monthly	X ^e
MRI Spine (ATRT only) Refer to Section Error! Reference source not found.	X	X		2 monthly ^f	X _{e,f}
FDG-PET/DOTATATE^g	X	X		2 monthly	X ^e
MIBG (Neuroblastoma only)		X	X	2 monthly	X ^e
CXR (ATRT only)	X	X ^h		End of therapy	
Abdominal Ultrasound (ATRT only)	X	X ^h		End of therapy	
MRI Brain (MRT only, not primary site)	X	X ^h		End of therapy	
CT Chest / CXR (Osteosarcoma only, non-lung primary)	X	X (CT and CXR)		2 monthly (CXR, CT and CXR at end of therapy)	X (CT or CXR)
Blood Samples – HDACi [Not applicable to United States]		Pretreatment	7 days after first dose		
Bone Marrow Evaluation (only if clinically indicated) including HDACi studies [Not applicable to United States]		X	End of Course	If positive at baseline or as clinically indicated	
Pregnancy Testⁱ		X			
ECG		X	End of Course	X	
Echocardiogram		X		6 monthly	

a If applicable and where available, these will be the last set of imaging investigations performed as part of routine patient care prior to salvage therapy.

b Up to 2 years from completion of therapy. c Not mandated at every time point, urinalysis performed per institutional practice.

d Use the same imaging modality throughout the course of the study e Follow-up imaging studies are not required if there is documented evidence of overt clinical progression. Follow-up imaging is 3 monthly or per routine follow-up.

f Repeat Spine MRI only if initially positive

g Use FDG-PET in non-CNS MRT.

Use FDG-PET in all osteosarcoma and neuroblastoma (if not MIBG avid).

Could be DOTATATE scans in neuroblastoma patients, when available, following discussion with Study Chair.

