4.5. CONCOMITANT THERAPIES

All medications and significant non-drug therapies will be recorded throughout the study period. This includes medications commenced from 14 days before until 28 days after the study drug is administered. Medications include both prescribed and over the counter (OTC) medications including herbal and vitamin treatments.

A listing of concomitant medications will include medication name and reason sorted by disease strata.

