5. ANALYSIS OF THE PRIMARY OUTCOME(S)

5.1. MAIN ANALYSIS

5.1.1. Event free survival

Primary Estimand

Population: All patients eligible and enrolled into trial with MRT/ATRT (strata 1), osteosarcoma (strata 2), or neuroblastoma (strata 3).

Treatment: Panobinostat

Outcome: Estimated 2-year Event free survival (EFS). EFS is calculated as the time from study enrolment to first documented disease progression, relapse or second malignancy, or death from any cause up to 2 years after study enrolment. The latest possible time of risk being 2 years after enrolment, or the last date known alive.

Summary measure: The probability of EFS (Kaplan-Meier) at with 95%CI will be estimated each stratum*. Kaplan- Meier curves will be plotted for EFS probability, enrolment date as start of risk period. Median EFS time will be calculated at 2 years post-enrolment.

**only calculated if stratum had adequate sample size (osteosarcoma and ATRT/MRT only).*

Subgroup Analysis:

Descriptive statistics (proportions) by subgroup for each disease strata.

Age at enrolment <36 months (3 years old) vs. ≥36 months

Radiation therapy (RT) vs. no RT

Disease status at trial entry (complete response vs stable disease)

Intercurrent Events

Potential intercurrent events:

Patient comes off study or treatment due to toxicity before an event is observed. Patient comes off study or treatment to receive another treatment.

Strategy for handling intercurrent event:

Treatment policy

EFS will be estimated for patients regardless of early treatment or trial termination. This approach assumes that data collected is reflective of those missing data (patients who withdrew from trial).

Sensitivity Analysis

Composite Strategy

Patients coming off study or protocol treatment due to an irreversible or unacceptable dose limiting toxicity or a Serious adverse event (SAE) before an event is observed, will be handled by the composite strategy. The removal from study/treatment date will be treated as an event.

Patients coming off study or protocol treatment to receive another treatment will also be handled by this strategy in the same analysis.

Primary Estimand Calculation

EFS will be estimated and visualised using the Stata sts list and graph commands.

```
stset tvar, fail(event) origin(time enrol_date) enter(time consent_date)
sts list, strata(disease type) risk table(6 12 24) sts graph, strata(disease type) risk
table(0 6 12 18 24) xlabel(0 6 12 18 24) tmax(24) Median EFS will be estimated

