5.1.2. Overall survival

Primary Estimand

Population: All patients eligible and enrolled into trial with MRT/ATRT (strata 1), osteosarcoma (strata 2), or neuroblastoma (strata 3).

Treatment: Panobinostat, dosing as per protocol.

Outcome: Estimated Overall Survival (OS). OS is calculated as the time from study enrolment to death from any cause.

Summary measure: The OS probability (Kaplan-Meier) and 95%CI will be estimated for each stratum* up to 2 years post-enrolment. Kaplan-Meier curves will be plotted for OS probability; enrolment date as start of risk period. The number of deaths and the median OS time will be reported up to 2 years post-enrolment.

**only calculated if stratum had adequate sample size (osteosarcoma and ATRT/MRT only).*

Subgroup Analysis:

As per section 5.1.1

Intercurrent Events

Potential intercurrent events:

Patient comes off study due to toxicity, or to start a new treatment.

Strategy for handling intercurrent event:

Patients coming off study due to a related toxicity or to start a new treatment will be handled with the treatment policy. OS will be analysed for all patients regardless of treatment received until last study visit.

Sensitivity Analysis

Composite Strategy

Patients coming off study due to toxicity or to start a new treatment before death could be observed will be handled by the composite strategy. The removal from study date will be treated as an event/death in sensitivity analysis.

Estimand Calculation

OS will be estimated and visualised using the Stata sts list and graph commands.

stset tvar, fail(death) origin(time enrol_date) enter(time consent_date) sts list,

strata(disease type)

sts graph, strata(disease type) tmax(24)

Median OS will be estimated using Stata stsum command *stsum,*

by(disease type)

Where time is in months and patients will be censored at their last known contact alive.

5.1.3 -Safety

Adverse events will be summarised by grade and type defined by CTCAE Version 4 from 1 week to 12 months after intervention commencement.

Relationship to study drug (definite, probable, possible) adverse events summarised in a table, with the worst AE grade reported by each participant.

A summary table of Dose Limiting Toxicities will include AE type, grade, and frequency.

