Course 3	mean(minmax)	mean(minmax)	X,X
Course 4	mean(minmax)	mean(minmax)	X,X
Course 5	mean(minmax)	mean(minmax)	X,X
Course 6	mean(minmax)	mean(minmax)	X,X
Course 7	mean(minmax)	mean(minmax)	X,X
Course 8	mean(minmax)	mean(minmax)	X,X
Course 9	mean(minmax)	mean(minmax)	X,X
Course 10	mean(minmax)	mean(minmax)	X,X
Course 11	mean(minmax)	mean(minmax)	X,X
Course 12	mean(minmax)	mean(minmax)	X,X

Table 7 – Panobinostat Compliance by Course and Disease strata

	Dose (mg/m ²)	Days Compliant	Total Days
MRT/ATRT	mean(min-max)	mean(min-max)	mean(min-max)
Osteosarcoma	mean(min-max)	mean(min-max)	mean(min-max)
	X, X	X, X	X, X

Neuroblastoma

Mean and range (min-max)

Listing 3: Concomitant Medication

Sorted by disease strata.

Disease Strata	Medication Name	Medication Reason
MRT/ATRT	X	X

MRT/ATRT	x	x
MRT/ATRT	x	x
Osteosarcoma	x	x
Osteosarcoma	x	x
Osteosarcoma	x	x
Neuroblastoma	x	x
Neuroblastoma	x	x
Neuroblastoma	x	x

Table 8 - Primary Endpoint: Event Free Survival**Primary Outcome- EFS**

MRT/ATRT	Osteosarcoma	Neuroblastoma
$x(95\%CI)$	$x(95\%CI)$	x
$x(min-max)$	$x(min-max)$	NA
$x(95\%CI)$	$x(95\%CI)$	x
$x(min-max)$	$x(min-max)$	NA
Proportion (95%CI)		
Proportion(95%CI)		
Proportion(95%CI)		

Overall EFS (95%CI)

Median EFS, months (95%CI)

Sensitivity Analysis - Composite Strategy

Overall EFS (95%CI)

Median EFS, months (95%CI)

Subgroup AnalysisAge at enrolment (<36 months vs. ≥ 36 months)

Radiation therapy (RT vs. no RT)

Up to 2 years post study enrolment

Table 9: Primary Endpoint: Overall Survival**Primary Outcome- Overall Survival**

MRT/ATRT Osteosarcoma Neuroblastoma

Disease status

	$x(95\%CI)$	$x(95\%CI)$	
Overall Survival (95%CI)			
Median overall survival, months (95%CI)			
Number of deaths	n	n	n
Subgroup Analysis			
Age at enrolment (<36 months vs. ≥ 36 months)	$Proportion (95\%CI)$	$Proportion (95\%CI)$	
Radiation therapy (RT vs. no RT)	$Proportion (95\%CI)$		
Disease Status	$Proportion (95\%CI)$		
Up to 2 years post study enrolment			

Table 10 - Treatment-Related Adverse Events

Treatment-Related Adverse Events

Toxicity (CTCAE v4.0)

	Any Grade	Event				
		Grade 1	Grade 2	Grade 3	Grade 4	event
Grade 4	$n(\%)$	n	n	n	n	event
event	$n(\%)$	n	n	n	n	event

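### The all-AE window closes 12 months after treatment start whatever the exposure, so it can take in 10 to 11 months off drug for early stoppers and leaves out later follow-up AEs

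*SAP*

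**What the plan says.** Section 2.2.1(c) gives the primary safety endpoint the window "Time Frame: 1 week to 12 months after intervention commencement". Section 5.1.3 repeats it for the analysis: "Adverse events will be summarised by grade and type defined by CTCAE Version 4 from 1 week to 12 months after intervention commencement". Neither place mentions last dose or new therapy, and neither limits the AEs by cause.

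Section 5.1.3 then adds a second output: "Relationship to study drug (definite, probable, possible) adverse events summarised in a table, with the worst AE grade reported by each participant". The Table 10 shell in Appendix A is headed "Treatment-Related Adverse Events", whereas the list of tables in section 9.2 names Table 10 as a general adverse event summary.

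Four other places bear on the point:

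- **Treatment length.** Sections 2 and 2.4 allow at most 12 courses of 28 days. Section 2.4 lists seven reasons for which treatment may end earlier.
- **AE collection.** In the section 2.7 schedule, the row "History (including AEs/DTs" is marked in the follow-up column. Footnote b sets follow-up as "Up to 2 years from completion of therapy". Patients who stop early were encouraged, not required, to keep attending.
- **Later therapy.** Section 5.1.1 names this intercurrent event: "Patient comes off study or treatment to receive another treatment". Sections 5.1.2 and 6.1.1 handle it too. Section 5.1.3 has no corresponding rule.
- **Concomitant therapies.** Section 4.5 includes medications started "until 28 days after the study drug is administered".

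**The concern.** Primary objective (b) in section 2.1.1 is to describe toxicity in patients on continuous dosing. A window that counts calendar time from first dose matches that aim only for a patient who stays on drug for nearly all of it. For a patient who stops after one or two courses, most of the window is time off drug, when AEs may come from the disease or from the next treatment. The all-AE incidence then mixes these with toxicity on panobinostat.

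The same cut-off works the other way for long-treated patients. AEs are on the follow-up schedule for up to two years after therapy, but the stated window closes about a month after their last dose. No listing in section 9.1 is set aside for AEs after that point.

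What is at stake is how the safety endpoint can be read. No test or decision rule in the SAP depends on it.

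**Working it through.** The SAP gives no figure for off-drug time, so there is none to reproduce. The size follows from date arithmetic.

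**Inputs**

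- Month and year lengths (section 3.7): 30.4375 and 365.25 days.
- Window end (sections 2.2.1(c), 5.1.3): 12 × 30.4375 = 365.25 days after treatment start.
- Course length and maximum number (sections 2, 2.4): 28 days, 12 courses, so 12 × 28 = 336 days.
- Follow-up (section 2.7): up to 2 years after therapy, 2 × 365.25 = 730.5 days.
- Time on drug of early stoppers: not given. I assume uninterrupted dosing and stopping at the end of a course, and show a range.

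**Off-drug time inside the window** = 365.25 − days on drug

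| Stops after | Days on drug | Off-drug days in window | Months |
|---|---|---|---|
| 1 course | 28 | 337.25 | 11.1 |
| 2 courses | 56 | 309.25 | 10.2 |
| 6 courses | 168 | 197.25 | 6.5 |
| 12 courses | 336 | 29.25 | 0.96 |

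**Follow-up outside the window** = days on drug + 730.5 − 365.25

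- 1 course: 28 + 365.25 = 393.25 days, 12.9 of 24 months.
- 2 courses: 56 + 365.25 = 421.25 days, 13.8 of 24 months.
- 12 courses: 336 + 365.25 = 701.25 days, 23.0 of 24 months.

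**With an end at last dose + 28 days**, off-drug time would be at most 28 days for every patient. A full-course patient would see almost no change (29.25 against 28 days). A one-course patient would go from 337.25 to 28.

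**Which AEs are counted.** The endpoint and the first sentence of 5.1.3 cover all AEs. The next sentence of 5.1.3 and the Table 10 shell cover related AEs. The section 9.2 title for the same table does not say. The off-drug problem bears mainly on the all-AE summary, and the SAP does not settle whether that summary or the related-AE table is the main output.

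**The case against.** The strongest reply is that the SAP already sorts AEs by cause. Section 5.1.3 plans a table by relationship to study drug, and the only general AE shell is limited to related events. AEs judged due to disease or next-line therapy would not appear there. This largely stands, and it limits the contamination. It does not remove it: the endpoint itself has no causality limit, and attribution is an investigator's judgement in an open-label, single-arm trial.

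Second, the 12-month window has a rationale. It covers the maximum treatment period plus about a month, and keeping off-drug time resembles the treatment-policy strategy chosen for the efficacy endpoints. The SAP is dated December 2024, three years after the last arm closed, so replacing the window of a primary endpoint now would itself be open to criticism. This stands, and it is why the 12-month summary should stay.

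Several stronger readings are tempting, and the document does not support them:

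- *Early stoppers do contribute many months of off-drug AEs.* They can. Whether they do depends on continued attendance, which was only encouraged, and on the protocol's AE reporting period, which is not at hand.
- *Later AEs cannot be sorted by cause because therapies are recorded only to 28 days after study drug.* Section 4.5 opens by saying that all medications and significant non-drug therapies are recorded over the whole study, and the 28-day sentence gives an inclusion, not a limit. Section 2.7 also collects the date and reason of early termination.
- *Every AE after month 12 is lost.* The window is attached to the all-AE sentence. The related-AE and DLT tables have no stated cut-off, so late related AEs are not clearly included and not clearly excluded. Second malignancy still counts as an EFS event up to 2 years after enrolment.
- *Comparison between strata is invalid.* None is planned for safety. Reporting is descriptive by stratum, and section 4.4 summarises exposure separately.

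**Conclusion.** The point holds in a limited form. The end of the all-AE window ignores exposure. It admits up to about 10 months off drug after 2 courses and about 11 months after 1, against 29 days for a patient who completes treatment. For that last patient, about 23 of 24 follow-up months lie outside it. The related-AE table reduces the first problem and does not clearly solve the second.

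These figures are possible time at risk, not counts of misplaced events. They assume uninterrupted dosing, stopping at the end of a course, follow-up counted from last dose, and continued attendance after stopping. The number of patients who stopped early is not in the document, so the practical effect is unknown. This is a cheap improvement to the safety section and does not invalidate the endpoint.

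**What to change.** Keep the 12-month summary as defined and add to section 5.1.3:

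1. **An exposure-based AE summary** running to 28 days after last dose, or to the start of another anti-cancer treatment if earlier. The 28 days are an analysis window borrowed from section 4.5. If the start date of the other treatment is not in the database, name the date that stands in for it.
2. **A listing** of treatment-related AEs, SAEs and second malignancies recorded after that date through follow-up, with time since last dose. Add it to section 9.1.
3. **One consistent description of Table 10.** The text of 5.1.3, the title in section 9.2 and the Appendix A shell should agree on whether all AEs or only related AEs are shown. If both are intended, give each its own table and state the window for each, including the relationship and DLT tables.

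The inputs should largely exist. Early-termination dates and reasons are collected (section 2.7), treatment days are summarised (section 4.4), and patients who leave for another treatment must already be identified for the composite analyses (section 5.1.1).

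The cost is some SAP wording, one more summary and one listing. The listing will be incomplete, because early stoppers were only encouraged to attend follow-up. The report should say so and should not present late AEs as an incidence.
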